## 5.0 THERAPEUTIC/DIAGNOSTIC AGENTS

LY3023414 will be supplied as 25-, 100-, or 200- mg capsules/tablets for oral consumption. LY3023414 capsules/tablets should be stored within the temperature range stated on the label. Investigators should instruct patients to store the capsules/tablets at home in the provided container and to keep out of the reach of children. Capsules/tablets should not be opened, crushed, or dissolved. LY3023414 will be labeled according to local regulatory requirements and supplied by the sponsor.

Lilly compound number: Chemical Name (CA Index Name):	LY3023414 2 H -Imidazo[4,5- c ]quinolin-2-one, 8- [5-(1-hydroxy-1-methylethyl)-3-pyridinyl]-1- [(2 S )-2-methoxypropyl]-3-methyl-
Other Names:	( S )-8-(5-(2-hydroxypropan-2-yl)pyridin-3- yl)-1-(2-methoxypropyl)-3-methyl-1 H -imidazo[4,5- c ]quinolin-2(3 H )-one
Molecular weight:	406.48
Molecular/Empirical Formula:	C 23 H 26 N 4 O 3
Description:	Practically white to light yellow solid
pKa:	4.92 and 3.75

pH:	5.79 (10 mg/mL suspension in water)
Specific Rotation	$[\alpha]_{436} - 42.09^\circ$ ; $[\alpha]_{589} 17.51^\circ$
Stability:	The drug substance is stable when stored at room temperature.
Solubility:	Water – Very slightly soluble Ethanol – Slightly soluble

Formulation: The drug product LY3023414 is supplied for clinical trial use as either 25-mg, 100-mg, or 200-mg capsules/tablets. The 25-mg capsules/tablets are an opaque white on the body and cap. The 100-mg capsules/tablets are an opaque blue on the body and cap. The 200-mg capsules/tablets are an opaque orangish-red color on the body and cap. Each capsule/tablet contains only LY3023414, with no inactive ingredients. The drug product is packaged in bottles and is stable when stored at room temperature conditions according to the label.

Labeling: Each bottle of LY3023414 will be labeled in accordance with current FDA and specific national requirements.

Storage condition for LY3022414 is 10-30°C (50-86°F).

**LY3023414 Dosing Information:** After the initial screening visit and registration in the study, patients will receive LY3023414 twice daily orally at a starting dose of 200mg.

**Drug Product Accountability:** Study drug for the study are provided by Eli Lilly and Company, Inc. and will be labeled as per the applicable regulations. Sites must request study drug by submitting an order form directly to the drug depot in order for the study drug to be shipped to the site pharmacy. The Investigator (or designee) will verify and acknowledge receipt of all study drug shipments by signing and returning all required forms.

All clinical drug supplies must be kept in an appropriate, limited access, secure place until used. Drug supplies will be counted and reconciled at the site. The study site will be required to maintain a log of the temperature where the study medication is stored.

All medication must be stored in a secure area under the proper storage requirements with access restricted to the site staff pharmacist or designee(s).

The Investigational medicinal product should not be used for any purpose outside the scope of this protocol, nor can Investigational medicinal product be transferred or licensed to any party not participating in the clinical study. Data for Investigational medicinal product are confidential and proprietary and shall be maintained as such by the Investigators.

The Principal Investigator (or an authorized designee) must maintain a careful record of the inventory of the Investigational medicinal product received using the Drug Accountability Form. The study drug will be destroyed as per MSKCC policy.

## 6.0 CRITERIA FOR SUBJECT ELIGIBILITY

### 6.1 Subject Inclusion Criteria

1. Patients must have recurrent or persistent endometrial carcinoma. Patients with the following histologic epithelial cell types are eligible: endometrioid adenocarcinoma, serous adenocarcinoma, undifferentiated carcinoma, clear cell adenocarcinoma, mixed epithelial carcinoma, adenocarcinoma not otherwise specified (N.O.S.), mucinous adenocarcinoma, squamous cell carcinoma, transitional cell carcinoma, and carcinosarcoma.
2. Age  $\geq 18$  years
3. Patients must have had at least one but no more than four prior chemotherapeutic regimens for management of endometrial carcinoma (including neo-adjuvant and/or adjuvant chemotherapy). Initial treatment may include chemotherapy, chemotherapy and radiation therapy, and/or consolidation/maintenance therapy. Chemotherapy administered in conjunction with primary radiation as a radio-sensitizer WILL be counted as a systemic chemotherapy regimen.
4. Patients tumors must have known PI3K pathway activation defined as EITHER of the following on a CLIA-approved molecular diagnostics test:
  - a. Genomic alteration resulting in loss of PTEN function including a whole or partial gene deletion, frame shift mutations, or non-sense mutations. Missense mutations in PTEN will not be considered qualifying.
  - b. A previously characterized activating mutation in any component of the pathway including: PIK3CA, AKT1, PIK3R1, PIK3R2, mTOR
5. Eastern Cooperative Oncology Group (ECOG) performance status of 0 or 1
6. Resolution of adverse effects of recent surgery, radiotherapy, or chemotherapy to Grade  $\leq 1$  prior to first study treatment (with the exception of alopecia or neuropathy).
7. Patients must have measurable disease. Measurable disease is defined by RECIST (version 1.1). Measurable disease is defined as at least one lesion that can be accurately measured in at least one dimension (longest diameter to be recorded). Each lesion must be  $\geq 10$  mm when measured by CT, MRI or caliper measurement by clinical exam; or  $\geq 20$  mm when measured by chest x-ray. Lymph nodes must be  $\geq 15$  mm in short axis when measured by CT or MRI.
8. No active infection requiring antibiotics (with the exception of uncomplicated urinary tract infection).
9. Any other prior therapy directed at the malignant tumor, including immunologic agents and radiotherapy, must be discontinued at least 2 weeks prior to first study treatment.
10. Adequate hematologic defined by the following laboratory results obtained within 14 days prior to first study treatment:
  - a. Absolute neutrophil count (ANC)  $\geq 1500/10^9$ dL
  - b. Platelet count  $\geq 100,000/10^9$ dL

- c. Hemoglobin  $\geq 9.0$  g/dL
- 11. Adequate hepatic function defined by the following laboratory results obtained within 14 days prior to first study treatment:
  - a. Total bilirubin  $\leq 1.5$  x the upper limit of normal (ULN)
  - b. AST and ALT  $\leq 3.0$  x ULN (unless the patient has Gilbert's Syndrome, in which case AST and ALT  $\leq 5.0$  x ULN is permitted)
  - c. Albumin  $\geq 3.5$  g/dL
- 12. Adequate renal function defined by the following laboratory results obtained within 14 days prior to first study treatment:
  - a. Serum creatinine  $\leq 1.5$  x ULN OR creatinine clearance  $\geq 50$  mL/min on the basis of the Cockcroft-Gault glomerular filtration rate estimation
- 13. For all patients (regardless of known diabetes) the following is required at screening:  
Fasting blood glucose  $\leq 135$  mg/dL (7.49 mmol/L) and HbA1c  $\leq 7.0\%$
- 14. For patients of childbearing potential, agreement to use two effective forms of contraception (e.g., surgical sterilization, a reliable barrier method, birth control pills, or contraceptive hormone implants) and to continue its use for the duration of the study and for 30 days after the last LY3023414 dose.
- 15. Patients must have been enrolled, or agree to consent to the companion genomic profiling study MSKCC IRB# 12-245.
- 16. Willingness to sign written informed consent to this study.

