Initial clinical LY3023414 pharmacokinetic/pharmacodynamic (PK/PD) data showed that LY3023414 maximum plasma concentration ( $C_{max}$ ) and area under the plasma concentration-time curve ( $AUC_{\infty}$ ) increased approximately dose-proportionally from 20 to 325 mg QD (that is within the QD dose range determined to be safe). However, the  $C_{max}$  and  $AUC_{\infty}$  increase was greater than dose proportional at 450 mg QD (i.e., that is at the dose exceeding the MTD). LY3023414 PK data following repeated BID dosing (dose range of 150 to 250 mg BID) were consistent with PK data following 20 to 325 mg QD. The oral clearance (CL/F) ranged from approximately 77 to 130 L/hour across the 20 to 325 mg dose range associated with an oral volume of distribution (V/F) ranging from 185 to 315 L in that same dose range. This clearance and volume lead to mean half-life ( $t_{1/2}$ ) of 2.07 hours (coefficient of variation [CV] = 45%, n = 35), consistent with the prediction.

The relative contribution of microsomal CYP-mediated clearance of LY3023414 was studied in vitro using human liver microsomes. Based on a substrate depletion approach, CYP 3A4 and CYP1A2 are responsible for 82% and 18% of hepatic CYP-mediated clearance of LY3023414, respectively. No in-vivo data are yet available.

The recent data from study CBBA indicate that LY3023414 is a weak inhibitor of CYP3A4. Concomitant administration of LY3023414 and midazolam lead to increase in midazolam exposure (fold increase: mean 1.459 [CV 30.5 %] [90% CI 1.21 – 1.76]). Hence LY3023414 may lead to increase in exposure of CYP3A4 substrate. Considering that CYP2C8, not CYP3A4, is the most relevant and major enzyme responsible for enzalutamide clearance and that the inhibitory effect of LY3023414 on CYP3A4 is weak, it is not anticipated that enzalutamide exposure will be significantly increased (i.e. > 1.5 fold change) after coadministration with LY3023414.

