## 6.2 Subject Exclusion Criteria

- 1. Patients with known concurrent activating RAS/RAF mutation or loss of function mutation or deletion in NF1 or NF2 resulting in MAP kinase pathway activation. Patients are not required to be evaluated for these alterations if not already performed.
- 2. Patients with diabetes requiring insulin or requiring more than one non-insulin hypoglycemia agents.
- 3. Patients previously treated with an mTOR, AKT, or PI3K inhibitor (including but not limited to GDC-0941, GDC-0980, BEZ235, BKM120, LY294002, PIK-75, TGX-221, XL147, XL765, SF1126, PX-866, D-87503, D-106669, GSK615, CAL101, everolimus, temsirolimus, and ridaforolimus). For agents not listed, the Study PI or Co-PI will make a determination.
- 4. History of myocardial infarction or unstable angina within 6 months prior to first study treatment.
- 5. New York Heart Association Class II or greater congestive heart failure.
- 6. Patients with a QTcF interval of  $>450$  msec on screening electrocardiogram (ECG)  
Note: If  $>450$  msec on the first ECG, 2 additional ECGs can be ordered same day and then the average may be used to determine eligibility.
- 7. History of malabsorption syndrome or other condition that would interfere with enteral absorption.
- 8. Inability or unwillingness to swallow pills
- 9. Clinically significant history of liver disease, including cirrhosis and current alcohol abuse.

10. Active hepatitis B or hepatitis C infection. Patients with previously resolved hepatitis B infection are eligible. Presence of positive test results for hepatitis B infection who have resolved the infection (defined by being positive for HB surface antibody (anti-HBs) and polymerase chain reaction (PCR) assay is negative for HBV DNA) are eligible. Patients positive for HCV antibody are eligible only if testing for HCV RNA is negative.
11. Known HIV infection.
12. Need for current chronic corticosteroid therapy ( $\geq 10$  mg of prednisone per day or an equivalent dose of other anti-inflammatory corticosteroids)
13. Pregnancy, lactation, or breastfeeding
14. Current severe, uncontrolled systemic disease (e.g., clinically significant cardiovascular, pulmonary, or metabolic disease)
15. Major surgical procedure or significant traumatic injury within 28 days prior to Day 1 or anticipation of the need for major surgery during the course of study treatment.

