16. Known untreated or active central nervous system (CNS) metastases (progressing or requiring anticonvulsants or corticosteroids for symptomatic control). Patients with a history of treated CNS metastases are eligible, provided that they meet all of the following criteria:
  - a. Presence of measurable disease outside the CNS
  - b. No radiographic evidence of worsening upon the completion of CNS-directed therapy and no evidence of interim progression between the completion of CNS-directed therapy and the screening radiographic study
  - c. No history of intracranial hemorrhage or spinal cord hemorrhage
  - d. No ongoing requirement for dexamethasone as therapy for CNS disease (anticonvulsants at a stable dose are allowed)
  - e. Absence of leptomeningeal disease
17. Inability to comply with study and follow-up procedures.
18. Any other disease, metabolic dysfunction, physical examination finding, or clinical laboratory finding that, in the investigator's opinion, gives reasonable suspicion of a disease or condition that contraindicates the use of an investigational drug or that may affect the interpretation of the results or render the patient at high risk from treatment complications.

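### Criterion 11 puts the Gilbert's syndrome exception on AST/ALT and leaves the bilirubin limit without one; 11a and 11b need to be reconciled

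*Combined protocol and SAP*

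**What the plan says.** Section 6.1, criterion 11 opens: "Adequate hepatic function defined by the following laboratory results obtained within 14 days prior to first study treatment". Two of its lines matter here.

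- 11a: "Total bilirubin $\leq 1.5$ x the upper limit of normal (ULN"). No exception is given for any patient.
- 11b: AST and ALT at or below 3.0 x ULN, "unless the patient has Gilbert's Syndrome, in which case AST and ALT" up to 5.0 x ULN are permitted.

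Gilbert's syndrome is mentioned nowhere else in the supplied text, and no other section relaxes the bilirubin limit.

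Three exclusions in Section 6.2 bear on the liver or on laboratory values:

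- Exclusion 9: "Clinically significant history of liver disease, including cirrhosis and current alcohol abuse".
- Exclusion 10: active hepatitis B or C.
- Exclusion 18: among other grounds, any "clinical laboratory finding that, in the investigator's opinion, gives reasonable suspicion of a disease or condition that contraindicates the use of an investigational drug".

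Section 15.1 requires a protocol-specific Eligibility Checklist at registration.

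**The concern.** Criterion 11 exists to define adequate liver function at entry. Gilbert's syndrome is a benign, isolated rise in bilirubin and does not raise AST or ALT. That is uncontroversial general medical knowledge, but the protocol does not state it. On that footing, an exception for Gilbert's has a rationale when attached to bilirubin and none when attached to transaminases. The plan relaxes the second and leaves the first fixed.

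Two things are at stake:

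- **Needless refusals.** A patient whose only abnormality is the bilirubin rise that Gilbert's explains gets no benefit from the exception. Section 7 reports that accrual was slow enough for eligibility to be widened, so such refusals have some cost.
- **Looser entry on a marker of liver injury.** For a Gilbert's patient the AST/ALT limit rises by two thirds (5.0/3.0 = 1.67), although the diagnosis does not account for a raised value. Table 11A has no row specific to transaminases or bilirubin; a rise on treatment would fall under its general rows or the general text after Table 11B. Entry screening therefore carries some weight.

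If the checklist copies 11b, both effects pass into practice.

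**Working it through.** The plan gives no figure for this point, so the check is to apply criterion 11 as a rule.

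**Inputs** (Section 6.1, criteria 11a and 11b): bilirubin limit 1.5 x ULN for all; AST/ALT limit 3.0 x ULN, or 5.0 x ULN with Gilbert's. The albumin limit in 11c is taken as met.

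**Rule:** pass if bilirubin ≤ 1.5 x ULN and AST/ALT ≤ L, where L = 5.0 x ULN with Gilbert's and 3.0 x ULN without.

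| Bilirubin (x ULN) | AST/ALT (x ULN) | Without Gilbert's | With Gilbert's |
|---|---|---|---|
| 1.0 | 1 | pass | pass |
| 1.5 | 3 | pass | pass |
| 1.5 | 4 | fail | **pass** |
| 1.5 | 5 | fail | **pass** |
| 1.5 | 5.1 | fail | fail |
| 1.6 | 1 | fail | fail |
| 2 | 1 | fail | fail |
| 3 | 1 | fail | fail |

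The two columns differ only where AST/ALT lies above 3.0 and up to 5.0 x ULN with bilirubin at or below 1.5 x ULN. On bilirubin, the Gilbert's clause changes no decision.

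**Can another criterion repair either result?**

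- *Refused for bilirubin above 1.5 x ULN.* Exclusions 9, 10 and 18 can only remove patients. None can admit someone who fails 11a.
- *Passed with AST/ALT above 3.0 and up to 5.0 x ULN.* Exclusion 9 needs a clinically significant history of liver disease, and exclusion 10 needs active viral hepatitis. Exclusion 18 can reach an unexplained laboratory value, but it depends on the investigator's opinion, and 11b expressly permits that value.

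**Could this be a text-extraction fault?** No. The clause itself names AST and ALT, so it has not slipped down from the bilirubin line.

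**Does it touch the primary test?** Section 14 sets n = 25 and success at 5 or more responses, against 10% and 30%. The exact binomial gives P(X ≥ 5 | 25, 0.10) = 0.098 and P(X ≥ 5 | 25, 0.30) = 0.910. These agree with the stated 10% and 90%, and neither uses the liver criteria.

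**The case against.** The case for treating this as a minor drafting query is a fair one.

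- **Other safeguards exist.** An unexplained AST of 4.5 x ULN is the kind of finding exclusion 18 covers. Hepatitis screening is required, and inclusion 6 requires effects of recent surgery, radiotherapy or chemotherapy to have settled to Grade 1 or less. This stands in part: such a patient passes criterion 11 but is not necessarily eligible overall. None of it helps the patient refused under 11a.
- **Intent is not stated.** 11a and 11b do not contradict each other, and the mismatch shows only with outside medical knowledge. This stands as a limit. The documents cannot show what the author meant, and 5.0 x ULN may have been intended for another condition.
- **The trial's inference is untouched.** Accrual runs until 25 evaluable patients are treated, so a refused patient is replaced. This stands.

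Two stronger readings are tempting, and the documents support neither.

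- *A reader might infer that every patient with Gilbert's is affected.* At an assumed prevalence of 3% to 10%, 25 patients would include 0.75 to 2.5 carriers (25 x 0.03 to 25 x 0.10). But carriers with bilirubin at or below 1.5 x ULN and AST/ALT at or below 3.0 x ULN are treated like anyone else. If 5% to 20% of carriers had AST/ALT in the wider band (also assumed), the count becomes 0.04 (0.75 x 0.05) to 0.5 (2.5 x 0.20). The documents give neither input. Patients refused on bilirubin are never enrolled, so 25 is not their denominator.
- *A reader might infer that the wider AST/ALT band means higher drug exposure.* Section 3.0 says "CYP 3A4 and CYP1A2 are responsible for 82% and 18% of hepatic CYP-mediated clearance of LY3023414", but that comes from human liver microsomes in vitro, and the text adds that in-vivo data were not yet available. The finding of mainly oxidative clearance in vivo rests on rat metabolites. Nothing links AST/ALT of 3 to 5 x ULN to exposure, and the related events and dose-limiting toxicities listed from the phase I study include no hepatic event. Section 10.0 also schedules bilirubin, AST and ALT through Cycle 1 and at each later cycle.

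**Conclusion.** The point holds as a wording error in eligibility. Read literally, the Gilbert's exception does nothing for bilirubin and changes decisions only for AST/ALT above 3.0 and up to 5.0 x ULN, a marker the condition does not explain. One group is refused with no route to admission. Another passes criterion 11 on values that would fail without the diagnosis, subject mainly to a discretionary exclusion.

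The conclusion rests on one premise from outside the documents: that Gilbert's is an isolated rise in bilirubin. The number of patients affected cannot be derived, because the documents give neither the prevalence of Gilbert's nor baseline liver-test values; with 25 evaluable patients it is probably small. Sample size, power and type I error do not change. The documents do not show that patients were harmed or that exposure would rise. The correction is worth making because the rule gives wrong eligibility decisions as written and is cheap to put right.

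**What to change.** The sponsor should reconcile 11a and 11b:

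1. State which test the Gilbert's clause is meant for, and move it to that line.
2. If 5.0 x ULN for AST/ALT was intended for a different condition, name that condition in 11b.
3. Leave any limit, and any supporting laboratory condition, to the sponsor's medical lead; none is proposed here.
4. Align the Eligibility Checklist with the amended text.

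The cost is a one-line amendment and a checklist update. The downside is that a Gilbert's patient with AST/ALT between 3 and 5 x ULN may no longer qualify on that ground.

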## 6.2 Subject Exclusion Criteria

- 1. Patients with known concurrent activating RAS/RAF mutation or loss of function mutation or deletion in NF1 or NF2 resulting in MAP kinase pathway activation. Patients are not required to be evaluated for these alterations if not already performed.
- 2. Patients with diabetes requiring insulin or requiring more than one non-insulin hypoglycemia agents.
- 3. Patients previously treated with an mTOR, AKT, or PI3K inhibitor (including but not limited to GDC-0941, GDC-0980, BEZ235, BKM120, LY294002, PIK-75, TGX-221, XL147, XL765, SF1126, PX-866, D-87503, D-106669, GSK615, CAL101, everolimus, temsirolimus, and ridaforolimus). For agents not listed, the Study PI or Co-PI will make a determination.
- 4. History of myocardial infarction or unstable angina within 6 months prior to first study treatment.
- 5. New York Heart Association Class II or greater congestive heart failure.
- 6. Patients with a QTcF interval of  $>450$  msec on screening electrocardiogram (ECG)  
Note: If  $>450$  msec on the first ECG, 2 additional ECGs can be ordered same day and then the average may be used to determine eligibility.
- 7. History of malabsorption syndrome or other condition that would interfere with enteral absorption.
- 8. Inability or unwillingness to swallow pills
- 9. Clinically significant history of liver disease, including cirrhosis and current alcohol abuse.

10. Active hepatitis B or hepatitis C infection. Patients with previously resolved hepatitis B infection are eligible. Presence of positive test results for hepatitis B infection who have resolved the infection (defined by being positive for HB surface antibody (anti-HBs) and polymerase chain reaction (PCR) assay is negative for HBV DNA) are eligible. Patients positive for HCV antibody are eligible only if testing for HCV RNA is negative.
11. Known HIV infection.
12. Need for current chronic corticosteroid therapy ( $\geq 10$  mg of prednisone per day or an equivalent dose of other anti-inflammatory corticosteroids)
13. Pregnancy, lactation, or breastfeeding
14. Current severe, uncontrolled systemic disease (e.g., clinically significant cardiovascular, pulmonary, or metabolic disease)
15. Major surgical procedure or significant traumatic injury within 28 days prior to Day 1 or anticipation of the need for major surgery during the course of study treatment.
16. Known untreated or active central nervous system (CNS) metastases (progressing or requiring anticonvulsants or corticosteroids for symptomatic control). Patients with a history of treated CNS metastases are eligible, provided that they meet all of the following criteria:
  - a. Presence of measurable disease outside the CNS
  - b. No radiographic evidence of worsening upon the completion of CNS-directed therapy and no evidence of interim progression between the completion of CNS-directed therapy and the screening radiographic study
  - c. No history of intracranial hemorrhage or spinal cord hemorrhage
  - d. No ongoing requirement for dexamethasone as therapy for CNS disease (anticonvulsants at a stable dose are allowed)
  - e. Absence of leptomeningeal disease
17. Inability to comply with study and follow-up procedures.
18. Any other disease, metabolic dysfunction, physical examination finding, or clinical laboratory finding that, in the investigator's opinion, gives reasonable suspicion of a disease or condition that contraindicates the use of an investigational drug or that may affect the interpretation of the results or render the patient at high risk from treatment complications.

